## 1- SYNOPSIS

Title	A phase I/II clinical trial to determine safety and feasibility of using an acellular human amniotic fluid (pAF) application to expedite healing of chronic wounds
Short Title	pAF for the Treatment of Chronic Wounds
IRB Number	IRB 00128708
IND	IND # 19330
Phase	Phase I/II
Design	This is a prospective randomized controlled study to determine the safety and feasibility of using processed sterile filtered amniotic fluid (pAF) to expedite healing in chronic wounds.
Study Duration	4 years
Study Center(s)	University of Utah
Objectives	
Primary Objective:
 
 
To determine the safety of using processed amniotic fluid (pAF) to treat patients with chronic wounds.
 
 
Secondary Objective:
 
 
To determine efficacy by examining a reduction in wound size after application of pAF compared to Standard of Care (SOC).
 

Number of Subjects	60 patients
Diagnosis and Main Eligibility Criteria	
Inclusion:
 
 
1. Patients 18-85 years old.
 
2. Patients with chronic upper and/or lower extremity wounds (including thermal) that are greater than 3 months, but less than 12 months old.
 
3. Patients with full thickness wounds.
 
4. Patients with at least one wound that is <math>\geq 5 \text{ cm}^2</math> and <math>< 75 \text{ cm}^2</math> in size.
 
5. Patient who is able to complete required site study visits and procedures in good faith
 
 
Exclusion:
 
 
1. Patients admitted to the hospital at the time of enrollment.
 
2. Patients who are pregnant, nursing or plan to become pregnant while participating in the study. If of child-bearing potential, unwillingness to use effective birth control while participating in the
 

	
study.
 
 
3. Suspicion of or diagnosis of osteomyelitis underlying the wound.
 
4. Patients who have received an investigational agent or intervention within the prior 30 days or plan to use within the study period.
 
5. Patient with sinus tracts, enterocutaneous fistulas or other epithelialized tracts.
 
6. Patients who require skin grafting.
 
7. Patients diagnosed with a highly disruptive, non-controlled mental health disorder (e.g., bipolar, or schizophrenia).
 
8. Patients with a history of prior drug abuse.
 

Study Product, Dose, Route, Regimen	
pAF will be delivered to the clinic on the date of application.  Dose is 1ml/5cm^2; Route: injected directly into wound; Limited to two injections.

Statistical Methodology	
The primary goal of the analysis is to demonstrate safety, which does not require statistical significance.
 
The secondary goal of the analysis is to assess efficacy by comparing percent reduction in wound area. Additional exploratory analyses will be conducted, such as subgroup analyses.

**2- OBJECTIVES**

**-Primary Objective:**

- The Burn Outpatient Clinic sees multiple types of wounds from burn to non-burn. The care of patients with chronic wounds is complex and difficult. To date, we have not found any treatments, including various dressings or other stem cell based therapies, which consistently reduce time of wound closure and improve pain. We would like to investigate the safety of using pAF to treat these wounds.

**-Secondary Objective:**

- We would like to determine efficacy of using pAF to treat chronic wounds by examining a reduction in wound size after application of pAF compared to Standard of Care (SOC).

**3- ENDPOINTS**

**-Primary Endpoint:**

- Whether the patient experienced any post-randomization, study-related SAEs while on study (up to Visit 5, defined later).

**-Secondary Endpoint:**

- The percent reduction in wound area at Visit 5 relative to the size at randomization visit.

#### **4- BACKGROUND AND RATIONALE**

The Burn Outpatient Clinic patient demographic includes 7-10% non-burn wounds per month. These wounds range from chronic venous stasis ulcers, pressure ulcers, diabetic foot ulcers, to rare genetically predisposed wounds. These wounds are slow to heal, they require large amounts of health care resources, and cause disability for the patient. We have yet to find a standard treatment modality or wound care regimen that consistently lessens time to wound closure, improves pain, and reduces scarring.

Human amniotic fluid and amniotic membrane have been used for many years in regenerative medicine. Literature review shows that amniotic fluid with the cellular components included and an additional study using granulized amniotic membrane with amniotic fluid have shown improved wound healing rates in select populations. Amniotic fluid contains cytokines, nutrients, and growth factors that are required for development of the fetus. Components of the amniotic fluid that make it important to wound healing include its anti-inflammatory properties (38%), immune regulation (25%) and anti-microbial properties (9%).

While amniotic membranes have been used for over 100 years in burns and other chronic wounds, amniotic fluid has not been rigorously studied. With the continuous rise of healthcare costs, price is another factor to consider with amniotic fluid and membranes. It is reported that the US spends more than 25 billion dollars annually on chronic wounds. This is on the rise due to the aging of the population and increases in obesity and diabetes. In an article titled "Wound Care Outcomes and Associated Costs Among Patients Treated in US Outpatient Wound Centers: Data from the US Wound Registry", it was estimated that the mean healing cost per wound ranged from \$3,927-\$9,358 depending on the type of wound. In other words, on average 2.6 - 6.3 million people require treatment for chronic wounds annually, a heavy toll for national healthcare costs.

[figure not shown]
The goal of our study is to assess, in an outpatient setting, the safety and healing in chronic wounds treated with pAF. We will include patients with upper or lower extremity full thickness wounds (including thermal) that are greater than 3 months old and less than 12 months old and who are able to complete required site study visits and procedures in good faith. The wound size must be greater than or equal to 5cm^2 and less than 75 cm^2. We will exclude anyone that is admitted to the hospital at the time of enrollment, is less than 18 years old or older than 85 years old, is known to be pregnant or planning to become pregnant (including women of childbearing potential who are unwilling to use effective birth control while participating in the study), is breastfeeding, has suspicion of osteomyelitis, has received or plans to receive an investigational agent or intervention, requires skin grafting, has wounds with sinus tracts, has a diagnosed highly disruptive uncontrolled mental health disorder, or has a known history of prior drug abuse. Our primary objective is to determine

the safety of using pAF to treat patients with chronic wounds and our secondary objective is to assess the reduction in wound size after application of pAF compared to standard of care.

Cases #1 & 2 show preliminary results that we have obtained with pAF applications when applied to refractory chronic wounds (>12 months without healing).

#### **Amniotic fluid (AF): Preclinical Data**

Early after conception and until the mother's water breaks for the delivery of their infant, the fetus is bathed in amniotic fluid. AF functions as a supportive cushion to the fetus and provides a protective environment. AF is a rich source of nutrients, cytokines and growth factors that are required for fetal development and maturation. AF also contains stem cells with the potential to differentiate along multiple cell lineages. The protective and regenerative properties of AF are achieved via the exchange of water and solutes with surrounding tissues. This is accomplished via the utilization of different pathways during the course of a pregnancy that likely contribute to changes in the composition of the AF with gestational age.

Early reports showing that concentrates of AF inhibit the development of peritonitis were among some of the first evidence that AF has protective biological properties. This was followed by a publication by Shimberg and co-workers that AF accelerates defense-repair mechanisms within damaged joints. Since these early publications, more sophisticated evaluations have revealed the presence of antimicrobial, immunomodulatory, and growth-promoting activities in AF, some of which are likely to contribute to its protective biological properties.

Reports about the antimicrobial activity of AF differ among investigators. It is reported that AF with low antimicrobial activity is associated with a high incidence of an infectious syndrome in pregnant women. Some studies show that AF is inhibitory, while others show no effect against the same microorganisms. Components with antimicrobial, antiviral and antifungal activity that are present in AF include lysozyme, peroxidase, transferrin,  $\beta$ -lysin, immunoglobulins and zinc-peptide complexes.

Immunomodulatory properties of AF are evident from studies showing that enteral feeding of AF suppresses the pro-inflammatory responses in preterm pigs with necrotizing enterocolitis. Growth promoting activities of AF are supported by animal studies as well as by in vitro studies. These studies show that AF can enhance neochondrogenesis, regenerate peripheral nerves and bone, accelerate re-epithelialization in corneas, and promote healing of human skin wounds. Some of the factors that are found in AF that may contribute to these activities could be inflammatory mediators that include, but are not limited to TNF- $\alpha$ , IL-6, IL8, and IL-10^20, trophic factors that include EGF, IGF-1, FGF, HGF and TGF- $\alpha$ , and HA (hyaluronic acid), an important factor in promoting re-epithelialization in human skin wounds.

Based on the hypothesis that nutrients, cytokines and growth factors contained in the non-cellular fraction of AF are useful for reparative and regenerative treatments in patients, Pierce et al. conducted a study at the University of Utah to address three issues. The first was to determine the feasibility of consenting and screening volunteer donors for the routine collection of AF from full-term pregnant women who were scheduled for Caesarean sections (C-sections), and to then process the AF for clinical application. The second aim was to develop a processing method that resulted in a cell-free AF preparation suitable for clinical application. The third goal was to gain a better understanding of the components of the processed AF (pAF).

Goal #1: AF was collected by the staff of the Department of Obstetrics/Gynecology at the University of Utah hospital and was processed by technical staff of the Cell Therapy and Regenerative Medicine (CTRM) facility at the University of Utah. Physician-executed abdominal incisions were performed through the abdominal and uterine muscles without cutting into the amnion membrane. Using a sterile suction catheter connected to a sterile MediVac suction container (Cardinal Health, Waukegan, IL), a blunt end insertion with the catheter was made through the amniotic membrane and the AF aseptically suctioned into the MediVac container. The container was labeled, wrapped in frozen Insul-ice mats (Fisher Scientific, Hanover Park, IL) and placed in a temperature-monitored shipper that was

validated for transport between 2- 8 °C. The AF was transported to the CTRM facility at the University of Utah. Upon arrival at the CTRM facility, the tissue was immediately placed into a refrigerator at 2–8 °C until processing occurred.

Goal #2: At the time of processing, the MediVac container with AF was aseptically placed in a biological safety cabinet and the AF was aseptically transferred into sterile centrifuge tubes. The total volume and gross appearance of the AF were recorded and samples removed for sterility testing, cell counts and other relevant testing. The AF was centrifuged, the supernatant was collected, and the AF underwent a proprietary filtration process to eliminate insoluble components and sterilize the AF. The resulting product, processed AF (pAF), was evaluated for total volume, fluid chemistry, total protein, and hyaluronic acid (HA) levels. Final pAF products were also assessed for their cellular content and protein profiles using quantitative antibody arrays.

To validate the above described approach for collecting (Goal #1) and processing (Goal #2) AF, 36 pregnant women consented and passed the donor screening criteria. AF was successfully collected and processed from 17 of these individuals. Median AF volumes were 70 mL (range 10–815 mL; n = 17) .

Goal #3: Fluid chemistries were similar among the 17 pAFs, but some differences were noted in HA levels and cytokine profiles. Cytokine arrays revealed that an average of  $304 \pm 20$  ng/mL (mean  $\pm$ SD; n=3) of 400 proteins tested were present in pAF, with a majority of cytokines associated with host defense. Some of the peptides encountered and classified according to their function are found in table 1.

**Table 1. A sampling of the proteins/peptides by annotation that we have identified in pAF**

Pro-inflammatory	OPN, PAI-I, CD163, RAGE, IL17, IL1R3
Host defense	IL-27, LAG-3, GITR, PD1
Innate Immunity	Galectin-3, TLR-2, Osteoactivin
Antimicrobial	TSP-1, lactoferrin, CXCL14, Trappin-2, CCL-28, MIG
Anti-inflammatory	IL1-ra, MBL
Embryonic development	DKK1, DKK3
Angiogenesis	VEGF R1, Transferrin, TIMP-2
Wound healing	OPN, PAPP-A, FAP

### **Experience with using pAF in Clinical Settings:**

pAF manufactured at the University of Utah has been clinically used in over 2000 applications for over 100 different conditions. A majority of treatments have been for wounds and burns. No unexpected and related adverse events have been directly associated with the injection or topical application of pAF in these previous uses (Table 2).

**Table 2. Number and Type of Clinical Applications that were treated with Processed Amniotic Fluid**

Description	Number of Applications
Burns (All anatomical areas, 2nd & 3rd Degree)	736
Wounds (Chronic, Acute, Ulcers, Necrotizing Fascitis, etc.)	949
Urology (urethral stricture, pyronies, etc.)	177
Orthopedics (Joints, tendonitis, tendon tears, carpel tunnel, etc.)	188
Spine (cervical, lumbar, sacral)	43
Occular (GVHD, dry eye)	101
GI (Strictures, Fistulas, )	50
TMJ (joint arthritis)	30
Neuropathy (nerves)	7
Other	50
Total	2331

## ELIGIBILITY CRITERIA

### Inclusion Criteria:

1. Patients who are 18-85 years old
2. Patients with chronic upper and/ or lower extremity wounds (including thermal) that are greater than 3 months, but less than 12 months old
3. Patients with full thickness wounds
4. Patients with at least one wound that is  $\geq 5 \text{ cm}^2$  and  $< 75 \text{ cm}^2$  in size
5. Patient who is able to complete required site study visits and procedures in good faith.

### Exclusion Criteria:

1. Patients admitted to the hospital at the time of enrollment
2. Patients who are pregnant, nursing or plan to become pregnant while participating in the study. If of child-bearing potential, unwillingness to use effective birth control while participating in the study.
3. Suspicion of or diagnosis of osteomyelitis underlying the wound.
4. Patients who have received an investigational agent or intervention within the prior 30 days or plan to use within the study period.
5. Patient with sinus tracts, enterocutaneous fistulas or other epithelialized tracts
6. Patients who require skin grafting
7. Patients diagnosed with highly disruptive, non-controlled mental health disorder (e.g. bipolar, or schizophrenia).
8. Patients with a history of prior drug abuse

## 5- STUDY DESIGN AND PROCEDURES

A written Informed Consent will be obtained from all subjects before any study-related procedures are executed. Subjects will be randomized into two groups at a 1:1 ratio. The randomization will employ random block sizes to limit the ability to predict the next subject's

treatment prior to randomization. Because of the random block sizes, it is not guaranteed that exactly 30 subjects will be randomized to each arm. There may be as few as 28 in the treatment arm (32 in the control arm) or as many as 32 in the treatment arm (28 in the control arm). Because of the modest number of overall patients and the anticipated slow accrual rate, stratification will not be used in the randomization procedure.

If a subject has more than one qualifying wound, the largest wound will be randomized to one of the two study arms (pAF or SOC) and included in the primary and secondary endpoint analyses. All other wounds will be treated with standard of care.

Whether a wound is randomized to pAF or SOC, many of the components of the treatment regimen are the same. The overall treatment is described, with differences unique to the pAF arm emphasized.

- Study Overview:
  - a. Visit 1:
    - i. Screening of subject and wounds for eligibility
    - ii. Informed consent
    - iii. Pregnancy Test (only applicable to women of childbearing potential)
    - iv. Subject/Wound evaluation and assessment including measurements (includes local cleansing and debridement if needed, digital image capture, manual measurements, and maximal wound depth)
    - v. Wound-associated pain assessment
    - vi. Laboratory tests:
      - 1. Parvovirus B19 serology and nucleic acid testing
      - 2. Complete blood count including platelet count with white blood cell (WBC) differential
      - 3. Chemistry panel to include aminotransferases, serum creatinine
      - 4. Hemoglobin A1c
      - 5. HLA Type 1 antibody (Only done on the first 10 patients enrolled)
      - 6. PT/INR
      - 7. PTT
      - 8. Wound cultures
    - vii. Standard Burn Center wound care treatment
    - viii. Schedule subject's next visit to occur within 6 weeks (+/- 1 week) of consent

If a subject's wound reduces in size greater than or equal to 50% between Visit 1 and Visit 2, or if the subject received any out-of-study investigational agent/intervention to the wound after Visit 1 but before Visit 2, the subject will not be randomized into the study and will be excluded. Because such subjects are not to be randomized, they are not considered enrolled and do not count towards the target enrollment of 60 subjects.

- b. Visit 2 (6 weeks +/- 1 week from Visit 1):

- i. Subject/Wound evaluation and assessment including measurements (includes local cleansing and debridement if needed, digital image capture and upload to the Burn Unit image storage, manual measurements, and maximal wound depth)
- ii. Wound-associated pain assessment
- iii. Wound cultures
- iv. Determination of whether largest qualifying wound is eligible for randomization (see note following Visit 5)
- v. If applicable, randomization of largest qualifying wound to pAF or SOC arm

**If in pAF arm,**

- 1. The amount of processed amniotic fluid to be injected into the randomized wound will be calculated based on the area of the wound (1ml/5cm^2).
- 2. To assist with discomfort, topical or injectable anesthetic will be applied to the wound based on standard dosing recommendations. Pliaglis (Lidocaine 7%, tetracaine 7%; emulsion cream) is the topical anesthetic applied 30-45 min prior to procedure in the clinic setting. If this is insufficient we will inject 1% lidocaine directly into the study site. All dosing is based on weight based recommendations in adults. Some patients may not need any of the above and some may require all.
- 3. The wound will be cleansed and debrided if needed prior to application of pAF and then prepped with chloraprep.
- 4. pAF is thawed and drawn into a 10ml syringe and, using a 25g needle, injected into the wound.
- 5. pAF is injected at the skin-wound base interface and base of the wound in a grid pattern (approximately 0.1 ml of pAF spaced evenly apart throughout the wound).
- 6. Standard burn center wound treatment regimen is applied to the wound per standard dressing care procedures (see *Standard Burn Center Wound Treatment Regimen* below).
- vi. Standard Burn Center wound care treatment of all other wounds (if any), including the wounds randomized to standard of care.
- vii. Schedule subject's next visit to occur 6 weeks (+/-1 week) later.
- viii. Subject will receive a follow-up phone call within 24 hours AND 5-7 days after visit to identify any adverse events that occur in relation to study participation and

record additional medications that were taken.

- c. Visit 3 (6 weeks +/- 1 week from Visit 2):
  - i. Subject/Wound evaluation and assessment including measurements (includes local cleansing and debridement if needed, digital image capture and upload to the Burn Unit image storage, manual measurements, and maximal wound depth)
  - ii. Wound-associated pain assessment
  - iii. Wound cultures

**If in pAF Arm**

1. The amount of processed amniotic fluid to be injected into the randomized wound will be calculated based on the area of the wound (1ml/5cm^2).
  2. To assist with discomfort, topical or injectable anesthetic will be applied to the wound based on standard dosing recommendations. Pliaglis (Lidocaine 7%, tetracaine 7%; emulsion cream) is the topical anesthetic applied 30-45 min prior to procedure in the clinic setting. If this is insufficient we will inject 1% lidocaine directly into the study site. All dosing is based on weight based recommendations in adults. Some patients may not need any of the above and some may require all.
  3. The wound will be cleansed and debrided if needed prior to application of pAF and then prepped with chloraprep.
  4. pAF is thawed and drawn into a 10ml syringe and, using a 25g needle, injected into the wound.
  5. pAF is injected at the skin-wound base interface and base of the wound in a grid pattern (approximately 0.1 ml of pAF spaced evenly apart throughout the wound).
  6. Standard burn center wound treatment regimen is applied to the wound per our standard dressing care procedures (see *Standard Burn Center Wound Treatment Regimen* below).
- iv. Standard Burn Center wound care treatment of all other wounds if any, including the wounds randomized to standard of care
  - v. Collect information on adverse events related to study participation.
  - vi. Schedule subject's next visit to occur 6 weeks (+/-1 week) later.
  - vii. Subject will receive a follow-up phone call within 24

hours AND 5-7 days after visit to identify any adverse events that occur in relation to study participation and record additional medications that were taken.

- d. Visit 4 (6 weeks +/-1 week from Visit 3):
  - i. Subject/Wound evaluation and assessment including measurements (includes local cleansing and debridement if needed, digital image capture and upload to the Burn Unit image storage, manual measurements, maximal wound depth)
  - ii. Wound-associated pain assessment
  - iii. If the wound(s) remains open, Standard Burn Center wound care treatment
  - iv. Laboratory tests:
    - 1. Parvovirus B19 serology and nucleic acid testing for subjects testing negative for Parvovirus at Visit 1.
    - 2. Complete blood count including platelet count with WBC differential
    - 3. Chemistry panel to include aminotransferases, serum creatinine
    - 4. Hemoglobin A1C
    - 5. HLA Type 1 antibody (Only done on the first 10 patients enrolled)
    - 6. PT/INR
    - 7. PTT
    - 8. Wound cultures
  - v. Collect information on adverse events related to study participation.
  - vi. Schedule the final study visit, 3 months (+/- 1 week) later.
  
- e. Visit 5 (3 months +/-1 week from Visit 4):
  - i. Subject/Wound evaluation and assessment including measurements (includes local cleansing and debridement if needed, digital image capture and upload to the Burn Unit image storage, manual measurements, and maximal wound depth). This assessment will include status of the wound and if it has closed since Visit 2, wound recurrence and hypertrophic scar formation (measured with modified Vancouver Scar Scale).
  - ii. Wound-associated pain assessment
  - iii. If the wound(s) remains open, Standard Burn Center wound care treatment
  - iv. Collect information on adverse events related to study participation.
  - v. Wound cultures

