**Table 3. PATIENT STUDY CALENDAR:**

	Visit 1 (Screening)	Visit 2 (6 weeks +/- 1 week from last visit)	Visit 3 (6 weeks +/- 1 week from last visit)	Visit 4 (6 weeks +/- 1 week from last visit)	Visit 5 (3 months +/- 1 week from last visit)
Informed Consent	X				
Eligibility	X				
Medical History	X				
Vitals (VAS, HR, BP, RR, O2 Sat, Weight, Height)	X	X	X	X	X
Randomization		X			
Physical Exam	X	X	X	X	X
Pregnancy Test	X 				
Injection of pAF (1ml/5cm  )- Treatment group		X	X		
Burn Center SOC	X	X	X	X	X
Manual Measurement	X	X	X	X	X
Pain Assessment	X	X	X	X	X
Laboratory Tests	X			X	
Wound Culture Swabs	X	X	X	X	X
Digital Image	X	X	X	X	X
Adverse Events Noted		X	X	X	X
Wound assessment	X	X	X	X	X

Follow-up phone call to assess adverse events		X 	X 		
---	--	----------------	----------------	--	--

Only applicable to women of childbearing potential

Follow-up phone call within 24 hours AND 5-7 days after visit to assess adverse events and medications.

Applicable study procedures may be completed via telehealth or by phone, at the discretion of the treating provider.

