### ASSESSMENT OF SAFETY:

Safety and tolerability will be evaluated by the PI and/ or trained physician from the results of reported signs and symptoms and scheduled physical examinations, for every follow-up visit. AEs will also be assessed by phone within 24 hours AND 5-7 days after Visit 2 and Visit 3 (injection visits). Unresolved AEs will be monitored for 1 year. More frequent safety evaluations may be performed if clinically indicated or at the discretion of the investigator. SAEs will be reported within 24 hours of discovery to the central Data Coordinating Center.

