## **7- SAFETY MONITORING**

### **Adverse Event Reporting**

The site investigator is responsible for evaluating all adverse events at their Clinical Center and ensuring that they are properly reported. Adverse events that occur during this study will be recorded. The nature of each experience, date and time (where appropriate) of onset, outcome, course, and relationship to treatment will be documented.

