### Classification of an Adverse Event (Relatedness, Severity, and Expectedness)

Relatedness: The suspected relationship between study interventions and any adverse event will be determined by the site investigator using the criteria below. Relatedness must be assessed by an investigator and may not be assessed by a research coordinator.

- Not Related: The event is clearly related to other factors, such as the subject's clinical state, therapeutic interventions, or concomitant drugs administered to the subject.

- Possibly Related: The event follows compatible temporal sequence from the time of beginning the assigned study intervention, but could have been produced by other factors such as the subject's clinical state, therapeutic interventions, or concomitant drugs administered to the subject.
- Probably Related: The event follows a reasonable temporal sequence from the time of beginning the assigned study intervention, and *cannot be reasonably explained* by other factors such as the subject's clinical state, therapeutic interventions, or concomitant drugs administered to the subject.

Severity: The severity, which is a measure of intensity, of clinical adverse events and laboratory abnormalities will be recorded by the site investigator and categorized. The following guidelines will be used to describe severity.

- Mild: The event requires minimal or no treatment and does not interfere with the participant's daily activities.
- Moderate: The event results in a low level of inconvenience or concern with the therapeutic measures. Moderate events may cause some interference with functioning.
- Severe: The event interrupts a participant's usual daily activity and may require systemic drug therapy or other treatment. Severe events are usually potentially life-threatening or incapacitating. Of note, the term "severe" does not necessarily equate to "serious".

***Expectedness of the Event: All adverse events, including serious adverse events, will be evaluated as to whether their occurrence was expected or unexpected. An AE will be considered unexpected if the nature, severity, or frequency of the event is not consistent with the risk information described for the study intervention. Expected adverse events for this study are:***

- ***Infection/ Cellulitis***
- ***Local bleeding***
- ***Purulent drainage***
- ***Inflammation***
- ***Rash***

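### All five adverse-event items in the protocol's visit lists ask for events related to study participation, whereas section 7 requires every adverse event to be recorded

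*Protocol*

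**What the plan says.** The visit-by-visit lists in Protocol section 5 contain five numbered adverse-event items:

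- Calls after Visit 2 (item viii), made within 24 hours and again at 5-7 days: "to identify any adverse events that occur in relation to study participation".
- In clinic at Visit 3 (item v), Visit 4 (item v) and Visit 5 (item iv): "Collect information on adverse events related to study participation".
- Calls after Visit 3 (item vii), on the same timing: "to identify any adverse events that occur in relation to study participation and record additional medications that were taken".

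Other parts of the protocol cover the same ground without the qualifier:

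- Table 3 marks "Adverse Events Noted" at Visits 2 to 5. Its second footnote describes the calls as "Follow-up phone call within 24 hours AND 5-7 days after visit to assess adverse events and medications".
- Section 6, Assessment of Safety: "AEs will also be assessed by phone within 24 hours AND 5-7 days after Visit 2 and Visit 3".
- Section 7, Adverse Event Reporting: "Adverse events that occur during this study will be recorded". The section's definition of an adverse event does not depend on attribution to the intervention. Its time-period text runs from consent to the last visit. Its data-collection text requires all events to be recorded, each classified by relatedness, severity and expectedness.
- Section 7, on who grades relatedness: "Relatedness must be assessed by an investigator and may not be assessed by a research coordinator". The grading scale includes a Not Related category.

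**The concern.** Section 7 treats relatedness as a property given to an event after it has been captured. The visit lists make it part of the question asked at capture. Someone who follows the lists literally would have to decide what is related before an investigator has seen the event, and might leave out whatever seemed incidental. The lists do not say who asks the question or makes the calls.

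Several planned outputs depend on capture that is not filtered in this way:

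- the occurrence of any adverse event (SAP 2.2.4);
- the occurrence of any unexpected adverse event (Protocol section 8; SAP 2.2.4 and 7.6.1);
- the adverse-event summaries for the DSMB (SAP 6.1) and the final ones (SAP 7.6.2).

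SAP 7.6.1 has expectedness noted for each recorded event, so an event that is never recorded cannot be counted as unexpected. The expected events listed in section 7 are infection or cellulitis, local bleeding, purulent drainage, inflammation and rash. An incidental illness outside that list could well be classed as unexpected, and it is also the kind of event a visit-list reader might think unrelated.

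**Working it through.** No formula or published figure is involved. The check is a count and a side-by-side reading.

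**Step 1. Items in the visit lists.** There are five. Three say related to (Visits 3, 4 and 5) and two say in relation to (the two call items). 3 + 2 = 5, so 5 of 5 carry the qualifier.

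**Step 2. Contacts covered.** In-clinic contacts are Visits 3, 4 and 5, which is 3. Calls are 2 per visit × 2 visits (2 and 3) = 4. The total is 3 + 4 = 7 scheduled contacts per subject, all qualified in the lists.

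**Step 3. The same contacts elsewhere.**

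| Contact | Visit lists | Table 3 | Section 6 |
|---|---|---|---|
| Visits 3, 4, 5 in clinic | qualified | unqualified | physician evaluation at every follow-up visit, unqualified |
| Calls after Visits 2 and 3 | qualified | unqualified | unqualified |
| Visit 2 in clinic | no item | marked, unqualified | not named |

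Table 3 marks 4 visits + 4 calls = 8 contacts, against 7 in the lists. The difference of one is Visit 2 in clinic.

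**Step 4. Which safety outcomes are exposed.** SAP 2.2.4 lists four outcomes besides the primary. Three do not depend on relatedness: any SAE, any AE and unexpected AEs. Protocol section 8 and SAP 7.6.1 each list three, of which two do not depend on it: any SAE and unexpected AEs. SAEs also have the reporting route in Monitoring Serious Adverse Events (section 7), which applies whatever the relatedness. Setting any SAE aside for that reason leaves 3 − 1 = 2 of 4 outcomes in SAP 2.2.4 (any AE, unexpected AEs) and 2 − 1 = 1 of 3 in each of the other two lists (unexpected AEs).

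**Step 5. Can the texts be read together?** Largely, yes. The data-collection text in section 7 is the dedicated rule and covers all events. The visit lists do not exclude unrelated events in terms. On that reading the lists are loosely worded and section 7 governs, but a person working from the lists is not told so.

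**The case against.** The strongest reply is that the protocol already settles the matter. The definition of an adverse event, the Not Related category and the data-collection text all show that unrelated events are to be recorded, and a prompt about related events does not cancel that rule. Section 7 also has adverse events reported immediately on discovery (Discontinuation of Study Drug). It separately requires unexpected medically attended events and new chronic illnesses to be recorded from consent. What staff actually ask is set by the case report forms, which are not available here. Most of this stands, and it is why the point is a wording conflict and not proof of lost data. It does not dispose of the point, because reporting on discovery depends on someone learning of the event, and the scheduled contacts are a main way of learning.

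Four stronger readings are tempting, and the documents do not support them:

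- *Section 5 as a whole restricts collection to related events.* Table 3 belongs to section 5, and its two adverse-event rows are unqualified. The conflict lies with the numbered visit lists.
- *The missing Visit 2 in-clinic item is a contradiction.* Table 3 also marks vitals, physical examination and medical history, and the lists name none of these. Leaving a marked procedure out of a list is normal in this protocol. Randomization takes place during Visit 2, so an item covering the period before it would not change any post-randomization outcome.
- *The any-SAE outcome would be under-counted.* The SAE route is not limited by relatedness and largely protects this outcome.
- *The primary endpoint is affected.* It counts study-related SAEs. The lists ask for related events, and SAEs also reach the medical monitor through their own route.

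**Conclusion.** The point holds as an internal inconsistency that should be corrected. All five numbered items, covering seven scheduled contacts per subject, frame the question by relatedness, against section 7, section 6 and Table 3. The outcomes mainly exposed are any AE and unexpected AEs, together with the adverse-event summaries. All of these are descriptive or exploratory.

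Confidence in the wording mismatch is high. The consequence is possible, not shown. It assumes that staff take the visit lists literally and that the case report form or call script does not already ask for all events. It falls mainly on non-serious events thought unrelated. The documents give no rate of missed events, so no effect size can be stated. The trial is unblinded (SAP 3.3), so a reader might infer that under-recording would differ by arm. Nothing in the documents shows that it would.

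**What to change.** In the five items (calls after Visit 2, item viii; Visit 3, item v; calls after Visit 3, item vii; Visit 4, item v; Visit 5, item iv), replace the relatedness qualifier with: *all adverse events since last contact, regardless of relatedness*. Check that the case report form and any call script use the same wording.

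As an optional tidy-up, repeat Table 3's Visit 2 mark as an item in the Visit 2 list. This would help only the recording between consent and Visit 2 that section 7 already requires.

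The cost is five wording edits and a check of the form and script. The downside is a few more unrelated events to record and classify. If section 7 governs, as it appears to, the edit adds no new requirement and changes no treatment rule.
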